**DATE:**

*Include the date of submission or revision.*

**REGULATORY FRAMEWORK:**

Please indicate all that apply (please note that the regulatory framework **does not** mean the funding source):

	DOD (Department of Defense)
	DOE (Department of Energy)
	DOJ (Department of Justice)
	ED (Department of Education)
	EPA (Environmental Protection Agency)
	FDA (Food and Drug Administration)
	HHS (Department of Health and Human Services)
	VA
	Other:

**FUNDING:**

This protocol is not currently funded.

**CLINICAL TRIALS**

Is this a clinical trial per the NIH definition of a Clinical Trial?  Yes  No

PROTOCOL TITLE: INTENSE: INvestigation of TENS Efficacy versus Posterior Tibial Nerve Stimulation for overactive bladder

NIH Definition of a Clinical Trial:

“A research study in which one or more human subjects are prospectively assigned to one or more interventions. An "intervention" is defined as a manipulation of the subject or subject’s environment for the purpose of modifying one or more health-related biomedical or behavioral processes and/or endpoints. Examples include: drugs/small molecules/compounds; biologics; devices; procedures (e.g., surgical techniques); delivery systems (e.g., telemedicine, face-to-face interviews); strategies to change health-related behavior (e.g., diet, cognitive therapy, exercise, development of new habits); treatment strategies; prevention strategies; and, diagnostic strategies (which may include placebo or other control) to evaluate the effects of those interventions on health-related biomedical or behavioral outcomes.”

**Use the following four questions to determine the difference between a clinical study and a clinical trial:**

- 1) Does the study involve human participants?  Yes  No
- 2) Are the participants prospectively assigned to an intervention?  Yes  No
- 3) Is the study designed to evaluate the effect of the intervention on the participants?  Yes  No
- 4) Is the effect being evaluated a health-related biomedical or behavioral outcome?  Yes  No

Note that if the answers to the 4 questions are yes, your study meets the NIH definition of a clinical trial, even if...

- You are studying healthy participants
- Your study does not have a comparison group (e.g., placebo or control)
- Your study is only designed to assess the pharmacokinetics, safety, and/or maximum tolerated dose of an investigational drug
- Your study is utilizing a behavioral intervention

If yes to all 4 questions, please confirm that the research team is familiar with and agrees to comply with the investigator requirement to register the study on the ClinicalTrials.gov database. Additionally, the approved consent document(s) must be uploaded to the ClinicalTrials.gov database  Yes  No

For any assistance with registration of your trial or the requirements, please contact [contact]

PROTOCOL TITLE: INTENSE: INvestigation of TENS Efficacy versus Posterior Tibial Nerve Stimulation for overactive bladder

## 1. Objectives

- 1.1. The objective of this research is to perform a non-masked, non-inferiority randomized controlled trial to assess the quality of life (QOL) of women with idiopathic overactive bladder (OAB) before and after treatment with percutaneous tibial nerve stimulation (PTNS) or transcutaneous electrical nerve stimulation (TENS) of tibial nerve. The target population is patients with OAB who previously failed first- and second-line treatments and desire non-surgical management.
- 1.2. Our central hypothesis is that a TENS unit is non-inferior to PTNS for improving the quality of life and symptom distress of women with OAB. The specific aims are:
  - 1.2.1. To compare the effects on health-related quality of life (HRQoL) and symptom bother as measured by the change in score from baseline of the Overactive Bladder questionnaire (OAB-q) in women with urgency urinary incontinence or overactive bladder before and after PTNS versus TENS after 3 months of therapy. Secondary outcomes related to this aim include change in symptom bother alone, as measured by the OAB-q symptom subscale and change in HRQL alone, as measured by the OAB-q HRQL subscale from baseline. **Hypothesis:** TENS will demonstrate similar effects on symptoms and symptom-associated HRQoL in the treatment of women with OAB compared to PTNS.
  - 1.2.2. To compare the rates of treatment success, as defined as 50% or more reduction of urinary incontinence episodes or 25% or more reduction in day or night voids in women with OAB before and after PTNS versus TENS after 3 months of therapy. The number of urinary incontinence episodes, number of voids per day and number of voids per night will be measured by a three-day voiding diary. **Hypothesis:** TENS will demonstrate similar rates of treatment success in women with OAB compared to PTNS.
  - 1.2.3. To perform a comparative analysis of patient satisfaction and compliance between TENS and PTNS. Patient satisfaction will be measured by a patient satisfaction question (PSQ). Patient compliance will be measured by number of treatment sessions completed as verified by clinical records of completed PTNS treatments and TENS device interrogation. **Hypothesis:** Women will be satisfied with both TENS and PTNS treatment and will have greater treatment compliance with TENS compared to PTNS.

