## 5. Number of Subjects

5.1. This is a single-center study at the University of New Mexico, therefore the total number of subjects at the University of New Mexico is the total number of subjects for the study.

5.2. The total number of subjects to be recruited at this site is up to 130 patients.

5.3. *Sample size calculation:* The primary outcome for this study is the change in the OAB-q total score from baseline to 3 months. We used the means and standard deviation for this questionnaire from an unpublished pilot RCT study from Walter Reed that compares PTNS and TENS for the treatment of OAB (unpublished work). We have powered the study based on a 10-point difference as significant between groups. This 10-point difference used for the power calculation is based on the previously established minimum important difference. To achieve power for this non-inferiority RCT study showing that the difference between groups is less than 10 points, we need 40 patients per group (80 total) to detect no difference with  $\alpha = 0.05$  and 80% power. Allowing for dropout of up to 30%, we will aim to randomize 114 patients, and will plan to recruit up to 130 to allow for potentially higher drop-out, as the study primary outcome is at the 12 weeks' time point. As we plan to perform both per-protocol and intention-to-treat analysis, the sample size must be met for both per-protocol and intention-to-treat analysis, with the per-protocol patients (those in the PTNS group completing at 12 treatments in a total of 13 weeks) being expected to be a lower sample size.

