## 7. Study Endpoints:

- 7.1. The **primary endpoint** of our study is to determine the change in OAB-q score in patients who undergo 12 weeks of PTNS compared to those who undergo TENS therapy for OAB. Our secondary endpoints include change in OAB-q Symptom Bother subscale score from baseline, change in OAB-q HRQL subscale score from baseline, number or urinary incontinence episodes, number of voids per day, number of voids per night, patient satisfaction question (PSQ) and patient compliance.
- 7.2. Due to the extremely low risk of the therapeutic interventions, we do not have any **safety endpoints**.
- 7.3. Our **exploratory endpoints** are to investigate compliance with treatment between groups and preference between therapeutic options.

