PROTOCOL TITLE: INTENSE: INvestigation of TENS Efficacy versus Posterior Tibial Nerve Stimulation for overactive bladder

given a 3-day voiding diary to complete prior to starting their intervention. Urinalysis and urine culture will be obtained to rule out urinary tract infection. This is routinely done on all new patients in our clinic and would be performed on patients not participating in the study as well. Data collected in addition to the above outcome measures includes patient demographics, medical/surgical history, and contact information, which are attached as supporting documents. This information will be collected from the patient on the day of enrollment and we will review the patient's medical record if information is missing or unclear.

The randomization sequence will be generated by computer-based randomization in a sequence that preserves 1:1 randomization and also preserves allocation concealment (likely with randomly alternating block sizes of 6-10 in blocked randomization). Randomization assignments will be completed via REDCAP by a research coordinator. Randomization will only occur after consent has been signed and all baseline data has been obtained.

*12.1. Interventions:*

*12.1.1. PTNS:* Women randomized to the PTNS group will begin therapy after their baseline evaluation is complete. They will be scheduled for PTNS treatment sessions once weekly for 30 minutes, for 12 weeks total. PTNS treatment will be performed as follows:

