### 13.Data Analysis

- 13.1. *Data Analysis:* Between and within group differences will be evaluated using Fisher's exact test for categorical variables and t-tests for continuous variables, as we expect the data will be normally distributed. Wilcoxon rank-sum test will be used for continuous variables that are not normally distributed. If there are any baseline differences between groups, a multivariate analysis will determine the contribution of these differences to observed differences (if any) between groups.
- 13.2. *Intention-to-treat analysis:* We plan to perform the primary analysis as "intention-to-treat" indicating that patients will be analyzed in the group to which they were randomized, regardless of compliance with study procedures, unless they asked to be withdrawn or were withdrawn by investigators due to safety or validity concerns. For example, PTNS patients that miss more than one session or do not make up a missed session of their office PTNS would still be analyzed in the "intention-to-treat" analysis as being in the PTNS group.
- 13.3. *Per protocol analysis:* We plan to perform a secondary analysis as "per protocol" indicating that patients will be analyzed in the group to which they were randomized only if they complete a full 12 weeks of treatment in compliance with study procedures, meaning that women assigned to the PTNS arm completed 12 weekly PTNS sessions in the office in 13 weeks or less, and women in the at-home TENS arm performed TENS stimulation at least 5 days per week for 12 weeks, as averaged over 12 weeks. For example, PTNS patients that miss more than one session or do not make up a missed session of their office PTNS will not be analyzed in the "per protocol" analysis as being in the PTNS group.
- 13.4. *Power Analysis:* Power analysis was performed based on previously reported means and standard deviation for the OAB-q. The primary outcome of this study is improvement in HRQL and symptom bother of OAB/UUI as measured by the OAB-q. We used the means and standard deviation for this questionnaire from a prior unpublished pilot RCT from Walter Reed comparing PTNS and TENS for the treatment of OAB. We have assumed a change score of greater than 10 points to be significant between groups based on the minimally important difference that has been previously established. To achieve significance for a non-inferiority study using these assumptions we would need 80 patients,

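### Diary success rate (aim 1.2.2): Fisher's test is too imprecise at 40 per arm to support 'similar' rates, and the diary counts have no prespecified baseline adjustment

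*Combined protocol and SAP*

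**What the plan says.** Section 1.2.2 sets the aim: "To compare the rates of treatment success, as defined as 50% or more reduction of urinary incontinence episodes or 25% or more reduction in day" (the 25% cut also covers nocturnal voids), before and after three months of therapy. A woman succeeds if she meets any one of the three. The hypothesis is that the rates will be similar. No margin, interval rule or power is attached to it.

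Section 13.1 names no test for this aim. Its general rule is Fisher's "exact test for categorical variables and t-tests for continuous variables", with the Wilcoxon rank-sum test where a continuous variable is not normally distributed. Adjustment by multivariate analysis follows only if the arms differ at baseline.

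Section 7.1 does not list the success rate. It lists incontinence episodes, "number of voids per day, number of voids per night" as secondary endpoints. It writes change from baseline for the two OAB-q subscales but not for the diary counts. Section 12 and its Table 1 have every woman complete a three-day diary at baseline, 6 and 12 weeks.

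The only sizing is for the OAB-q, in Section 5.3: "we need 40 patients per group (80 total) to detect no difference", the aim being "showing that the difference between groups is less than 10 points".

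**The concern.** Three counts, each measured before and after treatment, are reduced to one yes/no result, which discards information. In a superiority comparison, low power works against the sponsor's hypothesis. Here the hypothesis is similarity, so low power works in its favour: a weak test will often be non-significant even if TENS is worse. The counts in 7.1 could make up part of the loss, but as worded they may be compared at week 12 without the baseline diary that is already in hand. At stake is whether the diary results can tell the reader anything useful about TENS against PTNS.

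**Working it through.** **The plan's own figures.** Section 5.3 takes its SD from elsewhere ("We used the means and standard deviation for this questionnaire from an unpublished pilot RCT study") and does not state it, so the 40 per group cannot be reproduced directly. Solving n = 2·SD²·(z₁₋α + z₀.₈₀)²/10² for SD at n = 40:
- one-sided α 0.05: SD = 10·√20/(1.645 + 0.842) ≈ 18.0
- one-sided α 0.025: SD = 10·√20/(1.960 + 0.842) ≈ 16.0

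The dropout step is "Allowing for dropout of up to 30%, we will aim to randomize 114 patients": 80/(1 − 0.30) = 114.3, which agrees. With 1:1 allocation, 114/2 = 57 per arm and 130/2 = 65 per arm. None of this sizing concerns the diary.

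**Power of Fisher's test.** Full enumeration, two-sided 0.05. The documents give no success rates for this definition, so a PTNS rate of 50–70% is assumed.

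| TENS deficit | 40 per arm | 57 per arm | 65 per arm |
|---|---|---|---|
| 10 points | 11% | 14–15% | 16–18% |
| 15 points | 21–22% | 29–30% | 32–37% |
| 20 points | 37% | 50–51% | 54–59% |
| 30 points | 73–75% | 87–90% | 91–94% |

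Reaching 80% power takes a deficit of about 32–33 points at 40 per arm, or 27–28 at 57.

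**Width of the interval.** The 95% half-width is 1.96·√(2p(1 − p)/n). At n = 40 and p = 0.7 it is 1.96·√(0.42/40) = 0.20; at p = 0.5 it is 0.22. At n = 57 it is 0.17 to 0.18. An observed difference of zero at 40 per arm would leave a 20-point deficit inside or at the edge of the interval.

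**Adjusted counts against Fisher.** The documents give no diary means or SDs, so everything here is assumed:
- Baseline per day: 9 day voids, 2 night voids, 2.5 leaks; 20% of women continent.
- PTNS leaves 60%/80%/75% of leaks/day voids/night voids; TENS leaves 80%/92%/90% or 90%/100%/100%.
- Between-woman log-SD of response 0.15–0.30; occasion noise 0.05–0.15.

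The adjusted analysis is ANCOVA on the square-root week-12 count with the square-root baseline count as covariate. At 40 per arm, Fisher on the composite has 17–60% power. Gains of the adjusted count over Fisher, in percentage points of power:

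| Assumptions | Day voids | Leaks | Night voids |
|---|---|---|---|
| As listed, 1,500 trials per scenario | +12 to +29 | +6 to +21 | −7 to +6 |
| Baseline log-SD 0.6/0.25/0.4 (leaks/day/night), Poisson three-day counts, 500 trials | +7 to +26 | +11 to +16 | −4 to +7 |
| Same spreads, different noise model | +16 to +39 | −2 to +16 | −16 to +2 |
| Mix of responders (60% vs 30–40%) and non-responders | +5 to +22 | – | – |

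**Adjusted counts against unadjusted week-12 counts (t-test).** In the first set, leaks have 33–67% power adjusted against 15–32% unadjusted, and day voids 29–89% against 24–71%. In the second set, night voids have 26–59% against 21–52%. Adjustment wins for all three. For leaks, part of the gap is the square-root scale, and the Wilcoxon fallback in 13.1 would narrow it. In a separate leak-count simulation (success about 60% vs 39%, 40 per arm), Fisher had 40–44%, Wilcoxon on follow-up counts alone 46–60%, and baseline-adjusted log counts 60–66%.

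**Does adjustment establish similarity?** No. In a normal model with 60% PTNS success and a baseline/follow-up correlation of 0.3–0.7, ANCOVA at 40 per arm has 68–79% power for a 20-point deficit but only 44–55% for 15 points. A non-inferiority test of the success rate itself needs n = 2p(1 − p)(z₁₋α + z₀.₈₀)²/margin² per arm. For a 20-point margin that runs from 65 (p = 0.7, one-sided 0.05) to 99 (p = 0.5, one-sided 0.025).

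**The case against.** The strongest reply is that the diary evidence does not rest on Fisher's test. The counts are already secondary endpoints, tested by t-test or Wilcoxon. Baseline is not absent either: the diary is collected then, success is itself a reduction from it, 13.1 covers within-group differences, and it adjusts when the arms differ. Section 7.1 is a short list, and its silence on change may be loose wording. A responder rate is also easy to read clinically. All of this stands. What remains is that no baseline-adjusted comparison is prespecified for all women.

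Several stronger readings are tempting, and the documents do not support them:
- *Fisher is the least sensitive analysis in the plan.* Under the first set of assumptions, the unadjusted t-test on leaks has 15–32% power against 17–60% for Fisher.
- *A real deficit would generally be missed.* That depends on size. Around 20 points it is close to even at 57 per arm, and 30 points would usually be found. Section 5.3 wants the target met in the smaller per-protocol set as well, so the intention-to-treat set should exceed 40 per arm.
- *The plan will call a null Fisher result similar.* It nowhere says so; that is an inference from the hypothesis.
- *The yes/no endpoint is what invites that reading.* The main cause is the missing margin or interval rule, and better modelling alone does not supply one.

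**Conclusion.** The point holds as a loss of precision on a secondary aim. At 40 evaluable women per arm, Fisher's test finds a 15-point deficit about one time in five and a 20-point deficit just over one time in three (about 30% and 50% at 57 per arm). With an interval of about ±20 points, non-significance says little about similarity. These figures assume PTNS success of 50–70% and barely change across that range.

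The gain from baseline-adjusted counts rests on assumed diary values. It is clear for day voids (roughly 10–30 points of power in most scenarios), modest and assumption-dependent for leaks, and nil for night voids. Adjustment also improves on the unadjusted counts for all three. Because the trial is randomized, an unadjusted follow-up comparison is less precise, not biased. The OAB-q primary conclusion and its sample size are untouched.

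**What to change.** - In 7.1 and 13.1, prespecify for all women that each week-12 three-day count (leaks, day voids, night voids) is compared between arms with adjustment for the woman's own baseline count. Use negative binomial regression, or ANCOVA on the square-root count, and report the adjusted effect with a 95% confidence interval. Do not make adjustment depend on an observed baseline difference.
- Keep the success rate in 1.2.2, list it in 7.1, and report it as a risk difference with a 95% confidence interval.
- State that a non-significant test is not evidence of similarity, and that this aim is descriptive unless a margin is prespecified.

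The cost is wording and a little more analysis; no new data are needed. The downside is three count results to interpret together. The change should be made before any outcome data are examined.

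### Aim 1.2.2 hypothesises similar treatment-success rates, but the planned comparison is a Fisher test of difference with no margin or interval rule, so it cannot support that hypothesis

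*Combined protocol and SAP*

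**What the plan says.** Section 1.2.2 is a separate specific aim. It defines treatment success as a binary outcome taken from a three-day voiding diary: "50% or more reduction of urinary incontinence episodes or 25% or more reduction in day or night voids", compared "before and after PTNS versus TENS after 3 months of therapy". Its hypothesis is that "TENS will demonstrate similar rates of treatment success in women with OAB compared to PTNS".

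Section 13.1 gives the methods for all outcomes: Fisher's "exact test for categorical variables and t-tests for continuous variables", with a rank-sum test for non-normal data. If baseline differences appear, "a multivariate analysis will determine the contribution of these differences to observed differences (if any) between groups". No confidence interval is specified for any outcome.

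The only margin and the only power statement concern the OAB-q. Section 5.3 says: "We have powered the study based on a 10-point difference as significant between groups", and later "we need 40 patients per group (80 total) to detect no difference with" alpha 0.05 and 80% power. Section 13.4 repeats this. Neither section mentions the success rate, and section 7.1 lists the diary counts but not the responder rate among the secondary endpoints.

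Section 2 (Background) describes an earlier unpublished PTNS v TENS trial that found no difference, and discounts it as too small to establish equivalence or non-inferiority.

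**The concern.** Fisher's exact test takes equal rates as its null hypothesis. A small p-value is evidence against similar rates; a large one is not evidence for them. With no margin or interval rule, a non-significant result is the only planned result that could be offered in support of aim 1.2.2. The conditional multivariate analysis does not help, because it sets no margin either. The 10-point OAB-q margin cannot be transferred to a proportion, so tying the primary analysis firmly to that margin would leave this aim as it is.

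What is at stake is a secondary claim, but a visible one. The trial is unmasked and its primary outcome is a questionnaire. The diary-based success rate is the result readers would look to for corroboration. A non-significant p-value could be read as similarity, and dropout makes non-significance more likely.

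**Working it through.** **Inputs from the documents.** 40 evaluable per group, alpha 0.05 (sidedness not stated), 30% dropout, 114 randomised (5.3); maximum 130 (5.2); 1:1 allocation (section 12). 114/2 = 57 per arm, which is the evaluable number if nobody drops out of 114; 130/2 = 65.

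**Assumptions.** The PTNS success rate on this definition is not given, so I use 50-70% and show 30-90%. The test is taken as two-sided. The 20-point deficit is illustrative.

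**The plan's own figure.** The dropout step reproduces: 80/0.70 = 114.3, against 114 stated. The 40 per group cannot be reproduced because the SD is not printed. Solving n = 2·SD²·(z₁₋α + z₀.₈)²/10² for SD at n = 40:
- one-sided 0.025: 10·√20/(1.960 + 0.842) = 16.0;
- one-sided 0.05: 10·√20/(1.645 + 0.842) = 18.0.

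Either way it is an OAB-q calculation and carries no information about the success rate.

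**Chance that Fisher's test misses a 20-point deficit.** For each n, enumerate all 2×2 tables, mark those with two-sided p ≤ 0.05, and take 1 − Σ Bin(x; n, p₁)·Bin(y; n, p₁ − 0.20) over the marked tables, where p₁ is the PTNS rate.

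| PTNS v TENS | 40 per arm | 57 per arm |
|---|---|---|
| 50% v 30% | 63.2% | 49.4% |
| 60% v 40% | 63.1% | 50.5% |
| 70% v 50% | 63.2% | 49.4% |
| 80% v 60% | 59.2% | 41.9% |
| 90% v 70% (same for 30% v 10%) | 46.6% | 29.5% |

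With 65 evaluable per arm and PTNS at 50-70%, the miss rate is 41-46%. A one-sided Fisher test at 60% v 40% gives 54% (40 per arm) and 36% (57 per arm).

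**One concrete outcome.** An observed 24/40 v 16/40 (60% v 40%) gives a two-sided Fisher p of 0.12. The Newcombe 95% interval for TENS minus PTNS is about −39 to +2 points. The p-value says only that no significant difference was found; the interval shows that a deficit of up to 39 points is compatible with the data.

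**Precision of the difference.** Approximate (Wald) half-width = 1.96·√(2p(1 − p)/n), equal rates p in both arms:

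| Success rate | 40 per arm | 57 per arm |
|---|---|---|
| 50% | 21.9 points | 18.4 points |
| 60% | 21.5 points | 18.0 points |
| 80% | 17.5 points | 14.7 points |
| 90% | 13.1 points | 11.0 points |

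**What a margin on the rate would require.** With equal true rates, one-sided 0.025 and 80% power, n per arm = (1.960 + 0.842)²·2p(1 − p)/margin². For an illustrative 20-point margin this is 99 at p = 50% and 83 at p = 70%; for 15 points it is 147-175 over the same rates. The documents give no margin for the rate.

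**The case against.** Four points can fairly be made for the plan.

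- **The plan never says that p > 0.05 means similar.** A reader might infer that rule from the pairing of hypothesis and test, but 13.1 names a test and is silent on interpretation. Section 2 shows the investigators know the distinction, since they fault an earlier trial on exactly this ground. This stands: the supportable statement is that a null result could be read as similarity, not that it will be.
- **Similar may be an informal expectation.** The aim itself is to compare rates, and low power for a non-primary outcome is ordinary. This stands in part. Lack of power alone would not be an error. The defect is that a stated hypothesis is paired with an analysis that cannot support it.
- **The size depends on assumptions outside the documents.** A reader might take 50-63% as an unconditional miss rate. It is not: it needs PTNS success of about 50-70%, a two-sided test, a 20-point deficit, and 57 evaluable per arm for the lower end. That range of rates is at or near the worst case for each n. Success can be met by any of several components, so a higher rate is plausible and would lower the figure. This stands, and the range must be shown.
- **Fisher's test is not the only planned analysis.** The conditional multivariate analysis exists. This is correct, but it supplies no margin or interval rule, so the mismatch remains.

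**Conclusion.** The concern holds in this form: the hypothesis of similar success rates in 1.2.2 is matched to a test of difference in 13.1, with no margin, interval rule or power for the rate, so the planned analysis cannot support it. With a two-sided test and PTNS success of 50-70%, a true 20-point deficit is missed about 63% of the time at 40 evaluable per arm and about 50% at 57. Over PTNS rates of 30-90% the range is 30-63%. Even the lowest of these exceeds the 20% miss rate that 80% power would allow.

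The documents do not support the stronger conclusion that the investigators plan to declare similarity from a non-significant result. This is a secondary aim and does not affect the primary OAB-q comparison. The change should be made, but the trial does not depend on it.

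**What to change.** - **13.1:** make the primary report for aim 1.2.2 the risk difference in treatment success, TENS minus PTNS, with a two-sided 95% score-type confidence interval (Newcombe or Miettinen-Nurminen). State that a non-significant difference will not be interpreted as similarity.
- **1.2.2:** reword the hypothesis to match, as estimation of the difference in treatment success between arms.
- **13.4:** say that the trial is not sized to show similar success rates. If an expected precision is added, make it conditional on the assumed rate and label it approximate: half-width about 18-22 points at 50-60% success, 15-17.5 at 80%, and 11-13 at 90%, for 57 and 40 evaluable per arm.

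Setting a justified margin on the rate would be a legitimate alternative, but even a 20-point margin would need 83-99 evaluable per arm at 50-70% success, more than the 65 per arm that 130 women could give.

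The cost is wording in three places, with no new patients, visits or data. The downside is a more modest secondary claim: a difference with its interval in place of a statement of similarity.
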